7.6.4. Intensity criterion

The CTEP Version 4.0 of the NCI Common Terminology Criteria for Adverse Events (CTCAE) will be utilized for AE reporting. The CTEP Version 4.0 of the CTCAE is identified and located on the CTEP website at (http://ctep.cancer.gov/protocolDevelopment/electronic_applications/ctc.htm). All appropriate treatment areas should have access to a copy of the CTEP Version 4.0 of CTCAE.

The intensity of adverse events not listed in this classification will be assessed using the following descriptors:

- Mild (grade 1): does not affect the patient's usual daily activities,
- Moderate (grade 2): disturbs the patient's usual daily activities,
- Severe (grade 3): prevents the patient's usual daily activities,
- Very severe (grade 4): requires critical care / life-threatening,
- Death (grade 5).

7.6.5. New information

A new information is any new safety data that could lead to reevaluate the ratio between the

benefits and risks of the research, or that could be sufficiently important to consider modifications of the research documents, the research management or, if need be, the drug utilization.

7.7. Serious adverse events and new information notification (responsibility of the investigator) [Following Institut Bergonié procedures]

The investigator will notify the Vigilance Unit **without delay** about any serious adverse events or new events occurring:

- From the date of the informed consent is signed,
- During the whole patient follow-up period as defined by the research,
- Until 30 days after the end of patient follow-up period as defined by the research, if the event is likely to be research-related.

| Type of Event | Reporting procedure | Deadline for reporting to the sponsor |
|-----------------|---|---|
| SAE | SAE report form + written form if necessary | To be reported immediately to the sponsor |
| New information | Written report form | To be reported immediately to the sponsor |
| Pregnancy | Written report form | As soon as pregnancy is confirmed |

The investigator must complete the “*Serious Adverse Event Reporting Form*” ([Appendix HA](#)) immediately and assess the relationship with the study treatment. The form must then be dated, signed and sent by fax to the following address **without delay** to:

CELLULE DE VIGILANCE (VIGILANCE UNIT) - Unicancer
Fax : [name]
 Or Contact: R&D Unicancer – E-mail: [name]

For each event, the investigator will record:

- A description of the event that is as clearly as possible, using medical terminology,
- The date the event started and ended,
- The patient’s relevant medical history,
- The steps taken and whether or not corrective treatment was required, whether or not the investigational treatment was discontinued, etc.
- Concomitant medications / therapies
- The CTEP Version 4.0 of the NCI Common Terminology Criteria for Adverse Events (CTCAE) will be utilized for AE reporting. The CTEP Version 4.0 of the CTCAE is identified and located on the CTEP website at (http://ctep.cancer.gov/protocolDevelopment/electronic_applications/ctc.htm). All appropriate treatment areas should have access to a copy of the CTEP Version 4.0 of CTCAE.
- The causal link between this event and the trial treatment, disease treated or an intercurrent disease or treatment, or any obligation imposed by the research (a treatment-free period, additional examinations requested as part of the research etc.),

- Clinical course. If the event was not fatal, it should be monitored until recovery, until the patient has returned to his/her previous condition, or until any sequelae have stabilized,
- Whenever possible, the investigator must also attach the following with the serious adverse event report:
 - A copy of the hospitalization or extended hospitalization report,
 - A copy of the autopsy report, if required,
 - A copy of all the results of any additional tests performed, including relevant negative results, along with the normal laboratory values,
 - Any other document he or she considers useful and relevant.

All these documents must be anonymized.

Additional information may be requested (by fax, by telephone or during a visit) by the CRA and/or by the Vigilance Unit using the Data Query form.

The investigator is responsible for providing appropriate medical follow-up for patients until resolution or stabilization of the adverse event or until the patient’s death. Sometimes this may mean that follow-up will extend beyond the patient’s withdrawal from the trial.

The investigator keeps the documents about the presumed adverse effect so that the information previously sent can be added to if necessary.

The investigator responds to requests for additional information from the Vigilance Unit in order to document the original observation.

7.8. Non serious adverse events [Following Institut Bergonié procedures]

| TYPE OF EVENT | REPORTING PROCEDURES | DEADLINE FOR REPORTING TO THE SPONSOR |
|----------------|-------------------------|--|
| Non-serious AE | Case report/record form | Does not need to be reported immediately |

Non-serious adverse events will be reported by the investigator in the patient’s CRF and will be followed-up until complete resolution. The CTEP Version 4.0 of the NCI Common Terminology Criteria for Adverse Events (CTCAE) will be utilized for AE reporting. The CTEP Version 4.0 of the CTCAE is identified and located on the CTEP website at (http://ctep.cancer.gov/protocolDevelopment/electronic_applications/ctc.htm). All appropriate treatment areas should have access to a copy of the CTEP Version 4.0 of CTCAE.

If an adverse event becomes serious, it should be reported and followed-up as mentioned in the previous reporting procedures.

If the investigator would like to decrease trial treatment dose or temporarily stop study management without respecting protocol procedures, he/she should have previously discussed with the coordinator.

However, symptomatic treatment can be prescribed to manage the adverse event.

Any definitive interruption of the procedure has to be immediately notified to the sponsor. The patient remains in the study and is followed-up according to the procedures described in the protocol.

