| STUDY POPULATION Translational research study | All patients included in the trial are eligible for the translational research study. |
| NUMBER OF PATIENTS | Based on the following hypotheses under GDC-0449 treatment: 20% clinical benefit (null hypothesis), 40% acceptable clinical benefit (alternative hypothesis), 10% type I error rate, 90% power, a total of 37 assessable patients will be necessary (17 for the first stage + 20 for the second stage). In order to account for not assessable patients (+/- 20%), 45 patients will be recruited. |
| NUMBER OF SITES | This is a multicenter study. A complete list of investigators will be provided as a separate document. |
| STUDY DRUG FORMULATION | GDC-0449 – Capsules packaged in 75 mL bottles. Each bottle contains 32 capsules. |
| ROUTE OF ADMINISTRATION | GDC-0449: Oral |
| ADMINISTERED DOSE | GDC-0449: 150 mg, take with or without food at the same time every day |
| TREATMENT SCHEDULE | GDC-0449: Days 1-28 |

| | |
|---------------------------------------|--|
| EFFICACY EVALUATIONS | 
Patients will be evaluated for efficacy if they receive at least one complete or two incomplete cycles of GDC-0449, and if they have at least one disease measurement recorded not less than eight weeks after treatment onset (except for in case of early disease progression).
 
Antitumor activity will be assessed using RECIST on a set of measurable lesions identified at baseline as target lesions and followed until disease progression by the appropriate method (computed tomography [CT] scan or magnetic resonance imaging [MRI]).
 
Radiological and clinical (whenever appropriate) tumor assessment will be performed at baseline and every eight weeks until evidence of disease progression (PD). Whenever the criteria of response are met, the appropriate imaging tests will be repeated at least four weeks later in order to confirm the response. Beyond 48 months of treatment without evidence of progressive disease, radiological tumor assessment will be performed every 3 months.
 
Efficacy will be evaluated based on 6-month clinical benefit rate (primary objective), best overall response, 1- and 2-year PFS, and 1- and 2-year OS.
 |

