5.3 Duration of Therapy

In the absence of treatment delays due to adverse events, treatment may continue until one of the following criteria applies:

- Disease progression,
- Intercurrent illness that prevents further administration of treatment,
- Unacceptable adverse event(s),
- Patient decides to withdraw from the study, or
- General or specific changes in the patient's condition render the patient unacceptable for further treatment in the judgment of the investigator.

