5.4 Duration of Follow Up

Patients will be followed every 3 months until death or study discontinuation, whichever occurs first after removal from study or until death, whichever occurs first. Patients removed from study for unacceptable adverse events will be followed until resolution or stabilization of the adverse event.

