5.5 Criteria for removal from Study

Patients will be removed from study when any of the criteria listed in [Section 5.3](#) applies. The reason for study removal and the date the patient was removed must be documented in the Case Report Form.

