b: Serum or urine test 7 days prior to the first dose of GDC-0449 administration. Pregnancy test must be administered 24 hours prior to the start of therapy (serum) and at least once every month thereafter (serum or urine).
c: Off-treatment evaluation.
d: Tumor measurements are repeated every 8 weeks. Documentation (radiology) must be provided for patients removed from study for progressive disease. Beyond 48 months of treatment without evidence of progressive disease, radiological tumor assessment will be performed every 3 months.
e: After 6 cycles, blood test will be performed every two weeks (week 2 and week 4). Beyond 48 months of treatment blood test will be performed every 3 months.
f: After 25 cycles, physical exam (vital signs, weight, performance status) will be performed/evaluated every 3 months
Baseline evaluations are to be conducted within one week prior to start of protocol therapy.
Scans and X-rays must be done ≤ 4 weeks prior to the start of therapy.

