13. STATISTICAL CONSIDERATIONS

13.1 Study Design/Endpoint

We will rely on a two-stage Simon's design with the 6-month clinical benefit (CR + PR + SD) rate as the primary endpoint. At six months, patients will be classified as success (Alive at 6 months AND CR/PR/ SD) or failure (dead OR alive with progression).

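### Patients who stop drug without progression leave the study under Section 5.5 but stay in it under Section 7.8, so their 6-month tumour status may be missing, with no rule for counting them

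*Combined protocol and SAP*

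**What the plan says.** Section 5.3 lists five reasons for ending therapy: progression, intercurrent illness, unacceptable adverse events, the patient's decision to withdraw, and a change in condition as judged by the investigator. Section 5.5 attaches a study-level consequence to all five: "Patients will be removed from study when any of the criteria listed in" Section 5.3 applies.

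Section 7.8 points the other way. It opens with "Any definitive interruption of the procedure has to be immediately notified to the sponsor" and continues: "The patient remains in the study and is followed-up according to the procedures described in the protocol".

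On imaging, the synopsis (efficacy evaluations) ties the schedule to progression and not to treatment: "tumor assessment will be performed at baseline and every eight weeks until evidence of disease progression (PD". Section 5.4 describes what follows removal: "Patients will be followed every 3 months until death or study discontinuation". It mentions no scan. Footnote d of the Study Calendar (Section 10) adds "Documentation (radiology) must be provided for patients removed from study for progressive disease" and is silent on removal for other reasons.

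Section 13.1 defines the primary endpoint with two outcomes at six months: "success (Alive at 6 months AND CR/PR/ SD) or failure (dead OR alive with progression". Under Section 13.2 an eligible patient is evaluable after one complete or two incomplete cycles plus one disease measurement at eight weeks or later.

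**The concern.** Take a patient whose week-8 scan shows stable disease and who stops at month 3 for an adverse event. The synopsis schedule would bring further scans at weeks 16 and 24. A site working from Sections 5.5 and 5.4 would take the patient off study and make three-monthly contact, which should pick up a death but need not include imaging. A site working from Section 7.8 and the synopsis would keep scanning.

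At the first site the patient is evaluable under Section 13.2 and alive at six months, with tumour status unknown. Section 13.1 has no place for that patient, and the section on missing data (14.2.3) gives no rule for a missing tumour assessment. Whether the scan exists would depend on tolerability, on the patient's condition and on which section the site followed. The analyst would have to choose a convention after the data are in, for a decision that turns on 11 successes among 37.

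**Working it through.** **1. Which text covers a patient who stops for toxicity with stable disease?**

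| Source | What it implies |
|---|---|
| Section 5.5 | Removed from study |
| Section 7.8 | Remains in the study |
| Synopsis | Scans every eight weeks until progression |
| Section 5.4 | Contact every 3 months, no imaging named |
| Calendar footnote d | Radiology required only if removed for progression |
| Section 13.2 | Evaluable, given one scan at eight weeks or later |
| Section 13.1 | Neither success nor failure if unscanned at 6 months |

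**2. Reproduce the design.** Inputs from Section 13.2: null rate 0.20, target rate 0.40, 17 patients at stage 1 (stop at 3 or fewer), 37 in total (positive at 11 or more). With X1 the stage 1 successes and X2 the successes among the next 20,

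P(go | p) = sum over x = 4 to 17 of P(X1 = x) × P(X2 ≥ max(0, 11 − x)), where X1 ~ Bin(17, p) and X2 ~ Bin(20, p).

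This gives P(go | 0.20) = 0.0948 and P(go | 0.40) = 0.9033. A full search for Simon's optimal design returns the same 17/37 with cut-offs 3 and 10. The stated design is correct, provided that 6-month status is known for all 37.

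**3. Illustrate the loss.** Let u be the share of evaluable patients who stop without progression and have no 6-month assessment. The documents do not give u; 5-15% is an assumption. Assume also that these patients would have succeeded at the same rate p as the others (0.40 under the target, 0.20 under the null).

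- Counted as failures, the effective rate is p(1 − u).
- Carried forward as stable disease, so counted as successes, it is p(1 − u) + u.

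| u | Failures: rate under target | Power | Failures: rate under null | Type I error | Carried as SD: rate under null | Type I error |
|---|---|---|---|---|---|---|
| 5% | 0.38 | 0.858 | 0.19 | 0.071 | 0.24 | 0.238 |
| 10% | 0.36 | 0.799 | 0.18 | 0.051 | 0.28 | 0.436 |
| 15% | 0.34 | 0.726 | 0.17 | 0.035 | 0.32 | 0.638 |

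**4. In patients.** 0.05 × 37 = 1.85 and 0.15 × 37 = 5.55, so about 2 to 6 patients. At the cut-off one is enough: 11 of 37 is positive, and 10 of 37 is not.

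**The case against.** The best defence is that the conflict is one of terms. The list that Section 5.5 relies on sits under a heading about duration of therapy, and Section 5.4 goes on following patients after removal, so removal cannot mean the end of observation. Other text supports continued imaging. Section 11.1 repeats the eight-week interval with no on-drug limit. Section 11.1.4 asks for every effort to document progression after treatment stops. Section 11.1.8 has an independent radiologist review 6-month status, with sites sending the images. Section 13.5.2 has an unknown category, and the form in Appendix JC has a not-evaluable code.

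This narrows the point without closing it. Section 11.1 does not say that the interval survives removal. The sentence in 11.1.4 concerns symptomatic deterioration, not a stable patient who stops for toxicity. Section 11.1.8 presupposes a 6-month scan and does not require one off treatment. Neither the unknown category nor the not-evaluable code says how the patient enters the Simon count.

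Several stronger readings are not supported:

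- A reader might take Section 7.8 to keep the patient under the full on-treatment schedule. It refers only to the protocol's procedures, which could mean Section 5.4. It also sits under non-serious adverse events and is not shown to govern a patient who withdraws consent.
- A reader might cite the calendar's off-treatment column as proof that no scan is planned. The table is offered as an example and its layout is unreliable in the text available, so nothing here rests on it.
- A reader might say that PFS will be informatively censored. Sections 11.1.6 and 13.4 state no censoring rule, so this cannot be asserted.
- A reader might quote power of 44%. That needs 15% stopping and 80% of them truly progression-free (0.40 − 0.15 × 0.80 = 0.28, giving 0.436). It combines two extremes, the second at twice the target rate.

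Patients with no measurement at eight weeks or later are also not evaluable under Section 13.2. They fall under the roughly 20% recruitment allowance, so the earliest stoppers need not be among the 37.

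**Conclusion.** The point holds as a conflict in current text that bears on the primary endpoint. It is not an error in the sample size. If every site follows Section 7.8 and the synopsis, the data will be collected; if some follow Sections 5.5 and 5.4, 6-month status can be lost for patients who stop without progression and have not withdrawn consent.

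The size depends entirely on an assumed 5-15% unobserved. The two obvious conventions err in opposite directions. Counting these patients as failures costs roughly 5 to 18 points of power (90.3% to 85.8% or 72.6%) and is conservative for a false positive. Carrying them as stable disease takes type I error far past its limit. The failure convention is therefore the safer fallback, but it does not replace an outcome that the synopsis schedule would have recorded. This should be corrected; it does not undermine the design.

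**What to change.** - Reconcile Sections 5.4, 5.5 and 7.8 and calendar footnote d with the synopsis, so that stopping study treatment is distinguished from leaving the study. The tumour assessments already stated in the synopsis would then continue for a patient who stops without progression, until progression, death or withdrawal of consent. No reason for stopping treatment needs to change.
- State in Section 13.1 or 13.2 that an evaluable patient still without a 6-month assessment counts as a failure in both stages of the Simon rule.
- Record any new antitumour therapy started before 6 months, and show the primary result with those patients identified. Otherwise a patient stable at 6 months on another drug would count as a success of GDC-0449 with no way to see it.

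The cost is protocol wording plus off-treatment scans for about 2 to 6 patients under the same 5-15% assumption. On the synopsis's own wording those scans are already due.

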7.9. Pharmacovigilance Unit *[Following Institut Bergonié procedures]*

The Vigilance Unit of Institut Bergonié will analyze each SAE to define for the sponsor:

- Severity grading,
- Degree of relationship with study treatment,
- Whether expected or unexpected according the characteristics of study drug.

7.10. Notification and registration of unexpected serious adverse events and new information (Responsibility of the sponsor) *[Following Institut Bergonié procedures]*

The sponsor notifies unexpected serious adverse events and new information to the Regulatory Authorities (in person, or through an organization which has received allowances for this task) according to the usual notification procedures ([Appendix HB](#)).

8. PHARMACEUTICAL INFORMATION

A list of the adverse events and potential risks associated with the investigational or commercial agents administered in this study can be found in [Section 7.1](#).

8.1 GDC-0449

| | | |
|-----------------------------|--|--------------------------|
| Chemical Name: | 2-chloro- N -[4-chloro-3-pyridin-2-yl-phenyl]-4-methanesulfonyl-benzamide | |
| Other Names: | Systemic Hedgehog Pathway Antagonist, G-025897, G-025897.1, and GDC-0449.1 | |
| Classification: | Hedgehog Pathway Antagonist | |
| CAS Registry Number: | 879085-55-9 | |
| Molecular Formula: | C ₁₉ H ₁₄ Cl ₂ N ₂ O ₃ S | M.W.: 421.3 g/mol |
| Mode of Action: | GDC-0449 provides anticancer responses by inhibiting the Hedgehog pathway. The Hedgehog signaling pathway controls cell differentiation, growth, and proliferation. It is most active during embryogenesis but may also play a role in the regulation of adult stem cells involved in the maintenance and regeneration of adult tissues. | |
| How Supplied: | GDC-0449 is supplied by Genentech. It is available as 150-mg grey and pink, size 1 capsules containing microcrystalline cellulose, lactose monohydrate, sodium lauryl sulfate, povidone, talc, | |

sodium glycolate, and magnesium stearate. Capsules are packaged in 75-mL round, white, high-density polyethylene (HDPE) bottles and closed with 38/400 two-piece HDPE child-resistant caps. Each bottle contains 32 capsules.

Storage: GDC-0449 should be stored at room temperature between 59°F and 86°F (15°C and 30°C) and should be protected from excessive exposure to light.

Stability: Stability testing is ongoing.

Route of Administration: Oral

Drug Administration: Patients should take GDC-0449 at approximately the same time each day, with or without food. If a patient misses a dose (e.g., due to emesis), he or she should be instructed not to take or make up that dose and to resume dosing with the next scheduled dose. Missed doses should not be made up.

Patient Care Implications: The terminal half-life of GDC-0449 is approximately 10-14 days in healthy volunteers. If plasma levels of GDC-0449 need to be lowered emergently, animal studies suggest that oral administration of activated charcoal may lower drug plasma levels more quickly than dose cessation alone.

Drug Interactions: Caution should be exercised when dosing GDC-0449 with narrow therapeutic con-meds that are metabolized by CYP2Cs. Warfarin falls into this category (CYP2C9 substrate, narrow TI).

Availability

GDC-0449 is an investigational agent supplied to investigators by Almac Clinical Services .

8.1.1 GDC-0449 Ordering

Each participating institution will order GDC-0449 directly to the pharmacy of Bergonie Institute. ([name]: [contact], [contact]; email: [contact])

8.1.2 Agent Accountability

GDC-0449 Inventory Records – The investigator, or a responsible party designated by the investigator, must maintain a careful record of the inventory and disposition of all GDC-0449

using the NCI Drug Accountability Record Form (DARF) (http://ctep.cancer.gov/forms/docs/clin_drug_req.pdf).

9. CORRELATIVE/SPECIAL STUDIES

9.1. Laboratory Correlative Studies

9.1.1. External review of histology – Pathology Department Institut Bergonié

Collection, handling and shipping of Specimen(s)

Formalin fixed paraffin embedded tumor blocks **and** representative H/E (hematoxylin/eosin) slides must be sent to the reference pathologist **within 10 days of trial inclusion. If tumour blocks are not available for sending to the reference pathologist, just representative H and E slides can be sent for review.**

Pathology will be reviewed for all patients included in this trial.

Three forms will be used for this purpose and completed by the clinical investigator (the clinician who has registered the patient in the trial):

- **Form A (Appendix IA)** : Patient information transmitted to the local pathologist;
- **Form B (Appendix IB)**: Patient clinical data transmitted to the reference pathologist;
- **Form C (Appendix IC)**: Review form to be handled partly by the clinical investigator and partly by the reference pathologist.

The clinical investigator sends:

1. **Form A** (completed) to the local pathologist with a copy to :
 - the Data Center (Institut Bergonie, [name], [name], [name])
2. **Form B** (completed) and
3. **Form C** (upper part completed) to the reference pathologist

The local pathologist sends to the reference pathologist :

- 1 or 2 formalin fixed paraffin blocks (“Boin” fixation not allowed) and representative H and E Slides.
- his own report (including gross morphology, note necrosis)

The reference pathologist ([name]):

- Sends **Form C** (completed) to the Data Center with a copy to the local pathologist
- Retains 8 slides and the blocks for the correlative study

| |
|--|
| 
All material and documents will be sent to [name], Institut Bergonié, Service Pathologie [name] [name], France Tél : [name] – mail : [contact]
 |
|--|

Site(s) Performing Correlative Study

Reference pathologist : Pr [name], Institut Bergonie, Department of Pathology, [name], [name], [contact], [contact]

